STUDY PROTOCOL AND STATISTICAL ANALYSIS PLAN

Title: mHealth for Psychosis Help-Seeking

ClinicalTrials.gov Identifier: NCT05905601

Principal Investigator: [name].

Updated June 27, 2025

OVERVIEW

Study Objectives. A long duration of untreated illness is linked with poorer outcomes among youth experiencing early psychosis. While this population faces numerous barriers to in-person services (e.g. long travel distances, a lack of symptom recognition, stigmatizing attitudes toward help-seeking) most young people express interest in digital technologies to support their mental health. While multiple digital mental health interventions have demonstrated value in supporting self-management of individuals experiencing symptoms of psychosis, there is a need for new interventions designed for delivery to those who are not engaged with services but are seeking resources to learn more about their experiences online. The present study examines the acceptability, usability, and preliminary efficacy of the NORTH mHealth intervention, a mobile app designed to remotely and scalably provide support to young adults in need of evaluation or treatment for symptoms of early psychosis. This intervention, which was developed in a multi-phase user-centered design process, offers multimedia interactive content based on the principles of cognitive behavior therapy and motivational enhancement. Following an experimental therapeutics paradigm, this study examines two versions of the NORTH mHealth intervention: (1) NORTH “lite” – a version of NORTH that provides only self-management components, and (2) NORTH “full” – a version of NORTH that offers components designed to increase treatment motivation, including interactive psychoeducational information about diagnoses, treatments, and the treatment-seeking process. This study aims to examine whether the promise of mHealth can be leveraged to improve treatment-seeking attitudes and actions among this at-risk population.

Design. This is a parallel group randomized controlled trial design. Participants are randomized 1:1 to either NORTH “lite” or NORTH “full.” Randomization is stratified based on whether the individual had engaged in mental health treatment (per inclusion criterion i.e. either regular psychotherapy or antipsychotic medication) within the past year vs. longer than one year ago (or not at all). Primary outcome assessments are collected at (1) baseline, (2) 6 weeks after app installation, and (3) 12 weeks after app installation.

METHODS

Participants. Participants are 60 treatment-unengaged young adults experiencing psychosis symptoms indicating need for evaluation and/or treatment who meet the following criteria: (1) age 18-30, (2) living in the US, (3) owning an iPhone, (4) symptoms of psychosis as measured by both (4a) a score ≥ 20 on the Prodromal Questionnaire, Brief (PQB), (4b) a positive frequency average score ≥ 1.47 on the Community Assessment of Psychic Experiences (CAPE-P15), and (4c) a score ≤ 8 on the Moritz CAPE lie scale designed for online data collection, (5) less than five years since a first episode of psychosis or awareness of symptom onset, and (6) unengaged in specialty mental health services in the previous three months as defined either (6a) having taken a prescribed antipsychotic medication, (6b) or having attended regular psychotherapy. Exclusion criteria included (1) failure to accurately complete consent comprehension questions or (2) being unengaged in mental health services because of having completed or “graduated” from a specialty mental health program.

Recruitment. Participants are recruited through online study ads (i.e. Google, Instagram, and YouTube) as well as distribution through mental health advocacy organization and treatment websites and listservs.

Procedures. All screeners and study questionnaires are completed through online data capture (i.e. REDCap). Once participants click a link to the study landing page from a recruitment ad or posting, they are required to demonstrate understanding of study details through a comprehension questionnaire, provide informed consent and are subject to a series of steps to ensure eligibility for the study and identity verification. Study team members evaluate screening data and conduct

confirmatory synchronous screening by phone. The invitation to complete the baseline assessment is sent to participants after eligibility confirmation via text message. After baseline is complete, participants are invited to complete an installation session wherein they are introduced to their intervention, and oriented to study details. Participants are randomized to condition (via a pre-set stratified randomization algorithm, see above) at the time of the installation session.

Once participants have installed and been oriented to their study app, members of the study team are available to answer questions about study interventions or respond to concerns about the study. Up to three times during the study period, participants receive outreach via text message and phone call if they stopped using the app for five consecutive days (confirmed via app usage logs). This outreach assesses for technical issues or concerns from participants about app use. Subsequent assessments are sent to participants via text messages 6 and 12 weeks after they installed the NORTH app, and participants are also invited to complete weekly questionnaires to report actual treatment engagement frequency. Participants are compensated with \$60 gift cards for completing each assessment battery (or, in the case of baseline, baseline and installation session both).

Interventions. NORTH (Normalizing ORientation to Treatment and Help-Seeking) is a self-guided iOS mobile app designed to provide self-guided coping support to individuals experiencing early psychosis. It combines video, audio, and written text, and draws on principles of cognitive behavior therapy and motivational enhancement. While both NORTH “full” and NORTH “lite” contain lessons (i.e. introductory modules to new skills), practices (i.e. opportunities to practice skills through video coaching or written prompts), and tracking (i.e. rating changes in a well-being score over time), only participants with NORTH “full” receive in-app treatment-seeking and psychoeducational content. Note that all participants regardless of condition receive thorough materials about mental health symptoms, treatment options, and crisis resources. For participants in the NORTH “full” condition, treatment-seeking and in-depth psychoeducation is a focus of interactive mHealth content, whereas in the “lite” arm, only the self-management components can be found in-app.

Outcome Measures. Primary and secondary registered measures are listed below.

Measure	Construct	Description	Time Frame
Measure to Assess Steps to Service (MASS)	Change in Treatment Seeking Steps	Treatment seeking will be measured using the Measure to Assess Steps to Service (MASS). The MASS is a 17-item self-report assessment of steps taken towards the attainment of mental health treatment, including research, social support, and engagement with service provider steps. Each item is endorsed on a three-point Likert scale (0 = No, I have not done this, 1 = I have done this once or twice, 2 = I have done this multiple times). The MASS is scored by summing individual items with higher scores indicating greater levels of treatment-seeking actions.	Baseline, 6 weeks, 12 weeks
Endorsed and Anticipated Stigma Inventory (EASI) – Beliefs about Treatment / Beliefs about Treatment-Seeking subscales	Change in Treatment-related Attitudes / Beliefs	Help-Seeking Attitudes and Stigma will be measured primarily using the Endorsed and Anticipated Stigma Inventory (EASI). The full EASI is a 40-item self-reported questionnaire with subscales measuring beliefs about mental illness, beliefs about mental health treatment, beliefs about mental health treatment seeking,	Baseline, 6 weeks, 12 weeks

		
concerns about stigma from loved ones, and concerns about stigma from the workplace. The subscales are scored by summing the ratings from the eight individual items in each subscale (5-point scale with 1 = Strongly disagree, 5 = Strongly agree), with lower scores indicating less stigma, and more positive attitudes towards treatment and treatment-seeking.
 
The Beliefs About Treatment scale assesses individuals' beliefs about the efficacy and usefulness of mental health treatments. It is totaled as a sum, with higher scores indicating more stigmatizing attitudes toward treatment.
 
The Beliefs About Treatment Seeking scale assesses individuals' attitudes toward seeking mental health treatments. It is totaled as a sum, with higher scores indicating more stigmatizing attitudes toward treatment seeking.
	
Internalized Stigma of Mental Illness Inventory (ISMI-9)	Change in Internalized Stigma	The Internalized Stigma of Mental Health Inventory, Brief (ISMI-9) will provide additional insight into the strength of participants' internalized stigma of mental illness. The ISMI-9 is a nine-item self-report short form, where each item is rated on a four-point Likert scale (1 = Strongly disagree, 4 = Strongly agree) and totaled as a mean score. Thus scores range from 1 to 4 with higher scores indicating more severe internalization of mental illness stigma.	Baseline, 6 weeks, 12 weeks
Perceived Stress Questionnaire (PSQ)	Change in Perceived Stress	Perceived stress will be measured using the Perceived Stress Questionnaire (PSQ), which is a 30-item, self-report questionnaire that examines the experience of stress independent of a specific and objective occasion. Items are endorsed on a four-point scale (1 = Almost never, 4 = Usually), and are summed for a total score (ranging from 30 to 120), with higher scores indicating higher levels of perceived stress.	Baseline, 6 weeks, 12 weeks
Brief Resilience Scale (BRS)	Change in Resilience / Coping	The Brief Resilience Scale (BRS) will be used to assess resiliency. The BRS is a self-report form that consists of six resiliency statements that participants agree or disagree with on a five-point scale (1 = Strongly disagree, 5 = Strongly agree). Scores are totaled as a mean, and thus range from 1 to 5, with higher scores indicating greater resilience.	Baseline, 6 weeks, 12 weeks

Community Assessment of Psychic Experiences	Change in Symptoms	
The Community Assessment of Psychic Experiences (CAPE-42) will be used to assess positive, negative and depressive symptoms of psychosis. The CAPE-42 is a self-report, 42 two-part item assessment that measures both the frequency of experiencing symptoms (four-point scale, 1 = Never, 4 = Almost Always) as well as the distress level (four-point scale, 1 = Not Distressed, 4 = Very Distressed) associated with each endorsed symptom. The CAPE weighted score can be calculated by summing the frequency and distress item responses.
 
The positive subscale is 20 items and is totaled as a mean response ranging from 2 to 8, with higher scores indicating more frequent and distressing positive symptoms.
 
The negative subscale is 14 items and is totaled as a mean response ranging from 2 to 8, with higher scores indicating more frequent and distressing negative symptoms.
 
The depressive subscale is 8 items and is totaled as a mean response ranging from 2 to 8, with higher scores indicating more frequent and distressing depressive symptoms.
	Baseline, 6 weeks, 12 weeks
Choice of Outcome in CBT for Psychoses, Short-Form (CHOICE-SF)	Change in Recovery	
Recovery will be assessed using the Choice of Outcome in CBT for Psychoses, Short Form (CHOICE-SF). The CHOICE-SF is an 11-item self-report form developed to assess recovery-related goals for therapy. Participants rate themselves in different therapy-focused areas such as "self-confidence" or "ways of dealing with everyday stress" on a scale (0 = Worst, 10 = Best). Scores on the CHOICE-SF are totaled as mean score across all standard items, and thus range from 0 to 10 with higher scores reflecting improved recovery.
	Baseline, 6 weeks, 12 weeks
Sheehan Disability Scale	Change in Functioning	
Functioning will be measured using the Sheehan Disability Scale (SDS). The SDS is a short, five-item self-report form that assesses disability and functional impairment. The total score is the sum of three items measure to what extent symptoms have disrupted different aspects of daily life on a scale (0 = Not at all, 10 = Severely), thus the scale ranges
	Baseline, 6 weeks, 12 weeks

		from 0 to 30 with higher scores indicating greater functional impairment.	
Modified Usability Scale	Intervention Acceptability / Usability	Usability/Acceptability will be assessed with a modified version of the System Usability Scale derived from our group's previous work developing mHealth interventions. This composite measure, which comprises 26 items based on four measures - the System Usability Scale, Post Study System Usability Scale, Technology Assessment Model Measurement Scales, and Usefulness, Satisfaction and Ease Questionnaire - assesses participants' experiences with the intervention during the study period (1 = Disagree, 2 = Neutral, 3 = Agree). While this measure is often interpreted qualitatively by item, we will also compare the overall score, which will comprise an average and thus range from 1 to 3, with higher scores reflecting higher acceptability and usability.	6 weeks

DATA ANALYTIC PLAN

Clinical-trial data analyses. Linear regression will be used for continuous outcomes wherein participant and treatment condition are clustered as independent variables (i.e. adjusting for the baseline value of the outcome measure relevant to each model). We will separately model outcomes at 6 weeks and 12 weeks respectively. Within-condition changes will also be modeled using linear regression with assessment and value at baseline as independent variables. Effect sizes will be estimated using Cohen's d and 95% confidence intervals. Mean imputation is used to generate total scale scores consistent with measure convention (i.e. totaling sums or means) in instances when participants complete fewer than 50% of scale items. Descriptive outcome measures (i.e. measures of usability and acceptability) will be described qualitatively as well as compared with independent-samples t-tests. As this is a pilot trial with limited statistical power, we will model and interpret direction and size of effects for primary outcomes.

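### Do the weekly reports of actual treatment engagement need a stated status and summary in the analysis plan?

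*Combined protocol and SAP*

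**What the plan says.** The weekly forms appear once, in Procedures: "participants are also invited to complete weekly questionnaires to report actual treatment engagement frequency". The form's items, response scale and duration are not described.

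The Outcome Measures section opens with "Primary and secondary registered measures are listed below". The table that follows has no row for weekly engagement. Its rows are timed at baseline, 6 and 12 weeks, except usability, which is at 6 weeks only. The Design section puts the primary outcome assessments at baseline, 6 and 12 weeks.

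The Data Analytic Plan says "Linear regression will be used for continuous outcomes", "adjusting for the baseline value of the outcome measure relevant to each model", and "We will separately model outcomes at 6 weeks and 12 weeks respectively". On incomplete data it says only that "Mean imputation is used to generate total scale scores consistent with measure convention". It closes by saying that, as a pilot with limited power, the trial will interpret the direction and size of effects on primary outcomes.

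**The concern.** The stated aim covers treatment-seeking actions as well as attitudes, and the weekly form is the only measure described as recording how often treatment was actually used. It is therefore likely to be reported. Yet the plan does not say whether it is exploratory, how the weeks are combined, or what happens to weeks with no form.

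The general rule for continuous outcomes does not fill the gap:

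- It needs a baseline value of the same measure, and no baseline weekly report is described. Entry requires being "unengaged in specialty mental health services in the previous three months", so a baseline value on the same categories would vary little.
- It models weeks 6 and 12, which for weekly data could mean that week's form or all forms to date.
- Its imputation rule concerns items within a scale, not whole forms that were never returned.

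Different reasonable summaries can give different between-arm figures from the same reports. A choice made after seeing the data could then favour one arm.

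**Working it through.** The plan has no figure to reproduce here. The check has two parts: whether any planned result depends on the weekly data, and whether one summary is better enough to be required.

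**Part 1: dependence.** The actions part of the aim is carried by the MASS, a registered 17-item sum that includes steps of engagement with a service provider, graded never, once or twice, or multiple times. The attitudes part is carried by the EASI subscales. Both have baseline, 6-week and 12-week values and fit the stated regression. Neither uses the weekly form.

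**Part 2: choice of summary.** Inputs from the documents: 60 participants randomized 1:1, so 30 per arm. Assumed, because the documents are silent: 12 weekly reports, 30% engaged in both arms (9 per arm), no true arm difference, and the reporting rates below.

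1. *Single-week report.* With k engaged weeks placed at random, the number of engaged participants visible in one given week is 9 × k/12: 0.75 for k = 1, 1.5 for k = 2, 4.5 for k = 6. This loses information but creates no arm difference by itself.

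2. *Weekly response 80% v 60%, unrelated to engagement.* The share with any positive report is 0.30 × (1 − (1 − r)^k).
   - k = 1: 0.30 × 0.80 = 24.0% v 0.30 × 0.60 = 18.0%
   - k = 2: 0.30 × 0.96 = 28.8% v 0.30 × 0.84 = 25.2%
   - k = 6: 0.30 × 0.99994 = 30.0% v 0.30 × 0.9959 = 29.9%

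   Engaged weeks among returned reports are 0.30 × k/12 at either response rate (2.5% v 2.5% for k = 1). With equal response in the two arms, every gap is zero.

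3. *Early stopping, 10% v 40%.* Onset is uniform over weeks 1–12 and engagement then continues. A stopper's last report is uniform over weeks 1–11 (mean 6), so an engaged stopper shows it with probability 6/12.
   - Any positive report: 0.30 × (0.9 + 0.1 × 0.5) = 28.5% v 0.30 × (0.6 + 0.4 × 0.5) = 24.0%.
   - Each participant's own share of returned weeks: completers 0.30 × 6.5/12 = 0.1625, stoppers 0.30 × 7/24 = 0.0875. This gives 0.9 × 0.1625 + 0.1 × 0.0875 = 15.5% v 0.6 × 0.1625 + 0.4 × 0.0875 = 13.25%.
   - Linear model of all returned reports on arm, week and stratum, with errors clustered by participant: mean difference 0.0 points, 95% interval half-width about 15 points, coverage 94% (10,000 simulations, assuming 40% and 20% engaged in two equal strata).

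4. *Non-engaged weeks skipped more in one arm.* Same onset pattern. Engaged weeks are returned at 80% in both arms, and other weeks at 80% v 60%.
   - Any positive report: an engaged participant with m engaged weeks (m uniform on 1–12) is missed with probability 0.2^m, which averages 0.25/12 = 0.0208. So 0.30 × 0.979 = 29.4% in both arms, and the gap is zero.
   - Engaged weeks among returned reports: 16.25% in the first arm. In the second, 0.1625 × 0.8 = 0.130 and 0.8375 × 0.6 = 0.5025, giving 0.130/0.6325 = 20.6%. The spurious gap is 4.3 points.
   - The week, arm and stratum model gave a spurious gap of 3.8 and 4.0 points in two separate simulations.

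The ranking therefore reverses. In steps 2 and 3 missed forms are unrelated to engagement in that week, which is exactly what the all-reports model requires, so its zero bias is built in. In step 4 that assumption fails and the any-positive rule is the unbiased one.

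**The case for a change.** The best case for a change is that it would be cheap. Two or three sentences would label the data exploratory, name a summary and state how missed forms are treated, and would remove a choice that in steps 2 and 3 moves the arm comparison by 4.5 to 6 points. The trial already has a natural covariate: "Randomization is stratified based on whether the individual had engaged in mental health treatment". The factual part stands in full, since neither a status nor a summary is written anywhere.

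Three things weaken it:

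- The 6-point gap needs both unequal response and a single isolated week of engagement. An isolated week fits poorly with the entry categories of antipsychotic medication and regular psychotherapy. Procedures describes the same invitations and outreach for both arms, so nothing points to unequal response.
- Fixing a linear model now would mean specifying one for a form whose response scale and duration are not given, under a missing-report assumption that could be wrong in either direction.
- The gain depends on acting before the data are seen. The document was updated on June 27, 2025 and does not say how far collection had gone.

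The claim that any baseline value would be zero for everyone is also too firm. The psychotherapy criterion covers only regular attendance, and baseline and installation come after screening.

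**Conclusion.** No change to the plan is needed. The omission is real, but it is missing detail about supplementary data outside the registered measures. The MASS and EASI analyses are unaffected, and no stated rule gives a wrong result. Exploratory status follows by clear implication from the scope of the outcome table.

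The size of the effect is conditional throughout. Under assumed rates, an any-positive rule can show a gap of 0 to 6 points with no true difference, and an all-reports model 0 to about 4 points, depending on why forms are missed. In the early-stopping case the model's 95% interval is about 15 points either side, so with 30 per arm any result would be descriptive. No summary is shown to be better in general.

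An analyst who reports these data would ordinarily call them exploratory, choose one summary, give the number of forms returned by arm and state what is assumed about missed weeks. That fills the gap without an amendment.

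### The between-arm regressions leave out the randomization stratum: no bias, but a slightly over-wide 95% CI if allocation is balanced within strata and the stratum is prognostic

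*Combined protocol and SAP*

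**What the plan says.** The Design paragraph sets out a 1:1 parallel-group trial and states: "Randomization is stratified based on whether the individual had engaged in mental health treatment". The two levels are treatment within the past year, and treatment longer ago or none. The Procedures paragraph says that condition is assigned at the installation session "via a pre-set stratified randomization algorithm, see above". It does not mention blocks or any other device that forces balance within strata.

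The Data Analytic Plan specifies linear regression for continuous outcomes, run separately at 6 and 12 weeks, "adjusting for the baseline value of the outcome measure relevant to each model". The accompanying phrase about participant and condition being clustered as independent variables is unclear, but it cannot be read as including the stratum. No other section adds it.

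On reporting, the same section says "Effect sizes will be estimated using Cohen's d and 95% confidence intervals", and that because this is a pilot "we will model and interpret direction and size of effects for primary outcomes". It does not say whether d and its interval come from the regression or from group means and SDs.

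**The concern.** The trial balances its arms on one factor and then leaves that factor out of the analysis. When allocation is balanced within strata, the arms cannot differ by chance on the stratum, so the treatment estimate varies less than a model without the stratum assumes. The model counts stratum differences as residual noise, and its standard error is too large. The interval then covers more than 95% of the time and is wider than it needs to be.

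The trial has 60 participants and is to be read through the size of effects and their intervals, so interval width is what readers will use. Past-year treatment could plausibly predict treatment-seeking steps (MASS) and treatment beliefs (the two EASI subscales). The documents give less reason to expect this for stress, resilience, symptoms, recovery or functioning.

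**Working it through.** The plan gives no SD, stratum effect, stratum split, dropout rate or block size, and no derivation of the sample size. There is therefore no figure of its own to reproduce.

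**Inputs from the documents:** n = 60, 1:1 allocation, one binary stratum, regression on condition and baseline value, 95% CI.

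**Assumptions:** stratum effect d from 0 to 0.8 residual SD (the SD left within a stratum after baseline adjustment); share p of participants in one stratum, 0.5 or 0.2; baseline-outcome correlation r = 0.5; n = 45 as an attrition case.

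**1. Allocation balanced within strata.** Omitting the stratum adds n·p(1−p)·d² to the residual sum of squares, and the residual df are 57 instead of 56. The ratio of CI widths, omitted to included, is

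√(1 + p(1−p)·d²·n/(n−3)) × t57/t56, with t57 = 2.0025 and t56 = 2.0032.

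For p = 0.5 and d = 0.5: √(1 + 0.25 × 0.25 × 60/57) × 2.0025/2.0032 = 1.032.

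**2. Allocation not balanced within strata.** The usual standard error is then valid. Adding the stratum costs a little precision through chance imbalance, by a factor in variance of

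f = (t56/t57)² / (1 − 1/58) = 1.018.

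Adding it narrows the CI only if d exceeds √((f−1)/(p(1−p))). This is √(0.0183/0.25) = 0.27 for equal strata and √(0.0183/0.16) = 0.34 for a 20/80 split. At n = 45, f = 1.025 and the break-even points are 0.32 and 0.40.

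**3. Simulation.** Excess CI width from omitting the stratum, n = 60 (a negative value means that the model with the stratum has the wider CI):

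| Stratum effect (residual SD) | 0 | 0.2 | 0.3 | 0.5 | 0.8 |
|---|---|---|---|---|---|
| Balanced, equal strata | 0% | 0.5% | 1.1% | 3.2% | 8.0% |
| Balanced, 20/80 | 0% | 0.3% | 0.7% | 2.0% | 5.2% |
| Unbalanced, equal strata | −0.9% | −0.5% | +0.2% | +2.2% | +6.8% |
| Unbalanced, 20/80 | −0.9% | −0.6% | −0.2% | +1.1% | +4.1% |

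The balanced rows agree with the formula in step 1. With balance and equal strata, the mean half-width is 0.519 residual SD with the stratum. Without it, the half-width is 0.519, 0.522, 0.525, 0.536 and 0.560 across the five columns.

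**4. Error rates.** With balance, equal strata and the stratum omitted, type I error is 4.7, 4.6, 4.9, 4.2 and 3.5% across the same columns, so it becomes conservative as the effect grows. Without balance it stays at 4.7 to 5.3%. The mean estimate is within 0.005 of zero in every n = 60 cell. A separate simulation with blocks of 4 describes the stratum by the share of post-baseline variance that it explains. It gives coverage of 95.5 to 95.7% at a 5% share and 96.0 to 96.3% at a 10% share.

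**5. Where the CI for d comes from.** If it is built from group means and SDs, its width relative to the model CI with no stratum effect is about √(1/(1−r²)) × (t58/t56) × √(1 − 1/58). This gives 1.04, 1.14 and 1.39 at r = 0.3, 0.5 and 0.7. The calculation uses the same SD divisor for both and ignores that SD's own sampling error.

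**The case against.** The strongest reply is that nothing goes wrong. The interval errs in the cautious direction, the trial is a declared pilot, and no test or decision rule in the plan depends on where the CI ends. The stratum may also add little beyond baseline. Every participant is "unengaged in specialty mental health services in the previous three months", and baseline MASS already records steps "including research, social support, and engagement with service provider steps". At 0.2 to 0.3 SD, with balance and equal strata, the half-width changes by only 0.003 to 0.006 residual SD, which would alter nobody's reading.

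Attrition weakens the case further. With blocked allocation of 60 and 45 random completers, the excess width at 0, 0.2, 0.3 and 0.5 SD is about −0.4, +0.1, +0.8 and +2.7% for equal strata, and −0.4, −0.1, +0.3 and +1.6% for a 20/80 split. If allocation is not balanced, adding the stratum slightly widens the CI below the break-even effect. If d is computed from group means, the regression covariates do not touch the reported interval at all.

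All of this stands, and it sets the priority: the gain is conditional and probably small. It does not show that the omission is harmless in every plausible case, or that including the stratum is unsound. The possible loss is about 1%, and the possible gain is several times that if the stratum matters. The point about the source of d is separate, and over the likely range it is larger. It can be settled in the same sentence of the plan.

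**Conclusion.** The point holds. The plan stratifies on past-year treatment and leaves that factor out of both between-arm models. The estimate is unbiased and type I error is not inflated. With balance within strata and 60 participants, the CI is about 0 to 1% too wide for stratum effects up to 0.3 residual SD, 2 to 3% at 0.5 and 5 to 8% at 0.8. Without balance the CI is valid, and precision is lost only above 0.27 to 0.34 SD (0.32 to 0.40 at n = 45). These sizes rest on assumed stratum effects, splits and r = 0.5, and they apply only to a CI taken from the regression. Confidence is high in the omission and in the conditional arithmetic, but not in the size of the gain. It should be changed because the change is nearly free and makes the analysis follow the randomization.

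**What to change.** In the Data Analytic Plan, write the between-arm model at 6 and at 12 weeks as: outcome = condition + baseline value of the outcome + randomization stratum (treatment in the past year, yes or no). State that the reported Cohen's d is the adjusted difference divided by a pre-stated SD, for example the pooled baseline SD, and that its 95% CI comes from the same model. State also whether allocation is balanced within strata. The case is strongest for MASS and the two EASI beliefs subscales; use the same model for the other outcomes so that all follow the randomization. The descriptive usability t-test can stay as it is.

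The cost is wording only. The covariate is already collected for randomization, and residual df fall from 57 to 56 with 60 participants. If the stratum has no effect, the CI widens by about 0% with balance and complete data, about 0.4% with balance and 45 completers, and about 0.9% without balance (about 1.3% at n = 45).
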